Procedure	Pre-Treatment Days		Treatment Days			In House Post Treatment Days					Notes
	-2	-1	1	2, 4, 6, 8, 10, 12, 14	3, 5, 7, 9, 11, 13	15 (24 h)	16 (48 h)	17 (72 h)	18 (96 h)	19 (120 h)	
Admission to Unit	X										In a pandemic situation see Appendix 7 .
Discharge from Unit										X	In a pandemic situation see Appendix 7
Brief Physical Exam		X		X (Day 6)		X				X	Brief physical examinations may be made full and laboratory procedures may be repeated if needed at the discretion of the PI.
CSSRs				X (Day 12)						X	
Weight, BMI		X								X	
Vital signs		X	X	X			X		X	X	Vital signs to be performed pre-dose. Temperature will be monitored every day during study participation. For further detail, see Section 8.1.2
12-lead safety ECGs		X	X	X	X (Day 3)	X	X	X	X	X	ECG should be performed pre-dose on dosing days. ECG timepoints may be reduced in subsequent dosing groups. For further detail, see Section 8.1.4
Continuous ECG (full time matched baseline on Day-1)		X	X	X (Day 2 end of 24 h collection from Day 1 and Day 14)		X (end of 24 h collection from Day 14)					Continuous ECG monitoring from Day -1 to 24 h post dose on Day 1 and 14. ECG data extraction will coincide with PK sampling schedule at pre-dose, 1, 2, 3, 4, 5, 6, 7, 8, 9, 10, 12, 16 and 24 h post dose on Days 1,

Procedure	Pre-Treatment Days		Treatment Days			In House Post Treatment Days					Notes
	-2	-1	1	2, 4, 6, 8, 10, 12, 14	3, 5, 7, 9, 11, 13	15 (24 h)	16 (48 h)	17 (72 h)	18 (96 h)	19 (120 h)	
											Hours (h) relate to PK sampling post last dose
Testing for SARS CoV-2	X			X (Day 14)	X (Day 7)					X	2, 14 and 15 and on corresponding timepoints on Day -1. For further detail, see Section 8.1.4
Drug/alcohol/cotinine screen	X										An additional SARS-CoV-2 test will be performed approximately one week prior to admission to the unit. Weekly SARS-CoV-2 testing is required while in the unit (Days 7 and 14) and on discharge (Day 19). An approved molecular test (PCR) will be used. For further detail, see Appendix 7 and Section 8.1.3.
Haematology/Chemistry / Urine tests		X	X	X			X		X	X	For further detail, see Appendix 2
Pregnancy Test	X										Female participants only. For further detail see Appendix 2
VH3739937 Dose Administration			X	X	X						Once-daily oral dose from Day 1 to Day 14. Randomization to occur on Day 1 prior to dosing.
Meals	Per site usual practice										For meal instructions prior to dose, see Section 5.3.1

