All participants will have a screening visit within 28 days prior to first dose and a follow-up visit approximately 28 days after the last dose. All dosing will be conducted in a hospital based inpatient clinical trial unit. Study participants will be confined to the clinic from Day -2 until discharge. Additional outpatient visits will be required for all study parts. Flexibility of visit scheduling may be required if a pandemic situation applies (see Appendix 7). Otherwise, study assessments will be performed as indicated in the SoA presented in this protocol.

A summary of the overall study design, including proposed doses, sample size, and order, is presented in Figure 3 and Figure 4 below.

Figure 3 Phase 1 Study in Healthy Participants using planned doses of VH3739937 Part 1 and Part 2

A=Active; P=Placebo

QD = once daily; QW = once weekly

*= Period 4 may include participants from both Cohorts 1 and 2

Highlighted cohorts and treatment periods denotes completed

The doses shown in [Figure 3](#) above are intended to demonstrate general concepts relating to factors of escalation. The modelling and simulation implemented using the data currently available following oral administration of a suspension formulation in the fed state indicated the predicted efficacious dose for the daily dose is 25 mg and the weekly dose is 500 mg. Due to the observed half-life of ~90 h, the anticipated accumulation ratio following repeated daily and weekly doses is ~6-fold and 1.3-fold, respectively. Dosing will be conducted in accordance with safety and PK stopping criteria (Section [7.1.4](#)).

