The duration of dosing in Cohort 5 is to support up to 18-day dosing as an oral lead for the future SAD and MAD studies of the long acting formulation of VH3739937. This duration is to allow the identification of any early drug hypersensitivity reactions (HSR) which may occur before the administration of the long acting formulation. In each escalating dose cohort, 7 participants will be randomized to receive VH3739937 and 3 participants will be randomized to receive PBO. Details of the starting dose and dose escalations in Part 2 (MAD) are provided in Section 4.3.

Part 2 of the study was initiated once the single dose safety and preliminary PK data were evaluated in the SAD and the maximum exposure for the first MAD dose was covered by the SAD certain dose level. The potential minimally effective daily oral dose for VH3739937 with the suspension formulation was determined by the modeling and simulation utilising data for all doses in Part 1, as 25 mg, and is anticipated to be that which is predicted to provide a steady state $C\tau \geq 0.258 \mu\text{g/mL}$ in 95% of participants. More detailed information may be found in the IB Supplement [GlaxoSmithKline Document Number 2021 [RPS_CLIN_004025](#)].

Dose escalation in the MAD will not exceed 2-fold between cohorts 3 to 5 and will be driven by safety and PK stopping criteria (see Section 7.1.4). The 500 mg dose included in the MAD Cohort 6 was determined following modeling and simulation of PK data acquired in SAD treatment periods through to 640mg and in MAD Cohort 3. In addition, a dose will not be assessed in the MAD until the anticipated steady-state exposure (C_{\max} and $AUC(0-\tau)$ on Day 14) for that dose have been evaluated and shown not to have met safety stopping criteria in the SAD portion of the study (Part 1).

For Part 2 MAD Cohorts 3, 4 and 5, 24-hour continuous Holter/ECG recordings will be collected, on the day before the first dose (Day -1), Day 1, and Day 14 for extraction of ECGs paired with PK sampling. In addition, 12-Lead ECGs will be collected for Part 2 at timepoints indicated in the SoA.

Participants in Part 2 will have a screening visit within 28 days prior to first dose and a follow-up visit approximately 28 days after the last dose. Flexibility of visit scheduling may be required if a pandemic situation applies (see [Appendix 7](#)). Otherwise, study

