7.1.4. PK Stopping Criteria for SAD and MAD

In the SAD, the PK stopping criteria are based on mitigating any potential for Cmax mediated effects on ECG parameters. There were no ECG or other CV effects in a good laboratory practice (GLP) single-dose CV study in telemeterized dogs (Cmax = 9.82 $\mu\text{g}/\text{mL}$) and a 1-month GLP study in dogs (Cmax = 39.8). The stopping criteria is conservatively based on lower Cmax in the CV study in telemeterized dogs where there were no CV effects (9.82 $\mu\text{g}/\text{mL}$), equivalent to 21 $\mu\text{g}/\text{mL}$, when adjusted for protein binding. Protein binding is higher in human (93%) compared to dog (85%). If safety or PK stopping criteria are not met for the current/prior doses, dose escalation in Part 1 (SAD) will be stopped in the event that the Bayesian predicted probability is $>50\%$ that any participant's Cmax for the next subsequent dose will exceed 21 $\mu\text{g}/\text{mL}$ (the SAD PK stopping criteria).

In the MAD, the PK stopping criteria are based on AUC exposures where VH3739937-related microscopic findings were observed in the stomach of rats and dogs in the GLP 1-month oral toxicity studies. Corresponding Cmax exposures are expected to be below 21 $\mu\text{g}/\text{mL}$. A NOAEL was identified for microscopic findings in the stomach of rats at 10 mg/kg/day and a LOAEL in rats was identified at 40 mg/kg/day. A NOAEL for microscopic findings in the stomach of dogs was not identified and the LOAEL in dogs was 3 mg/kg/day. At the LOAEL in rats and dogs, VH3739937 was well tolerated and resulted in minimal, reversible single cell necrosis of parietal cells and chief cells. Exposure at the LOAEL in rats was AUC = 96.2 $\mu\text{g}^*\text{h}/\text{mL}$ and in the dog was AUC = 51.9 $\mu\text{g}^*\text{h}/\text{mL}$. The LOAEL in rats was chosen as the PK stopping criteria, and exposure is approximately 4-fold higher than the AUC in rats at the NOAEL dose of 10 mg/kg/day. The selection of the higher LOAEL AUC from the two preclinical species arises from the need to achieve sufficiently high exposures for cardiodynamic assessment of the TQT prolongation risk and mitigate the need for a TQT study. In the absence of data on the effect of intrinsic and extrinsic factors on the PK of VH3739937, and at the time of study initiation, the typical targeted doses were ~ 4 x the minimal predicted efficacious dose.

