4. ANALYSIS POPULATIONS

Population	Definition / Criteria	Analyses Evaluated
Screened	
 • All participants who were screened for eligibility 	
 • Study Population
Enrolled	
 • All participants who passed screening and entered the study. • Note screening failures (who never passed screening even if rescreened) and participants screened but never enrolled into the study (Reserve, Not Used) are excluded from the Enrolled population as they did not enter the study. 	
 • Study Population
Safety	
 • All randomized participants who received at least one dose of study treatment. • Participants will be analyzed according to the intervention they received. 	
 • Study Population • Safety
Pharmacokinetic (PK)	
 • The PK Population will include all participants who undergo plasma or urine PK sampling and have evaluable PK assay results. 	
 • PK analyses

Refer to [Appendix 10](#) which details the population used for each display.

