8.2. Exploratory Pharmacokinetic Analyses

Exploratory analyses to assess the exposure response relationship between VH3739937 and QTcF following single and repeated administration (Part 1 & 2) will be conducted. Linear regression models using exposure as the independent variable and change from baseline in QTcF as the outcome variable will be run separately for Part 1 and 2.

$$y_{\delta QTcF} = \beta_0 + \beta_1 X_{Concentration}$$

The model estimates $\hat{\beta}_0$ and $\hat{\beta}_1$ and their 95% confidence intervals will be reported, and the regression line will be overlayed on the plot of the comparison of change in QTcF and concentration.

**9. POPULATION PHARMACOKINETIC (POPPK)
ANALYSES**

The population PK analysis and pharmacodynamic analyses are exploratory endpoints that will be performed under a separate RAP and reported separately from the main clinical study report (CSR).

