4.17.	PK	PK_F1	Scatter Plot of Individual QTcF Change from Baseline vs Time Matched VH3739937 PK Concentration – Part 2	Non-Standard Figure see shell at end of RAP, Reference study mid207187 Figure 5.2	SAC [1]
4.18.	PK	PK24	Individual VH3739937 Plasma Concentration-Time Plots (Linear and Semi-log) – Weekly Dosing Cohort 6	Include all timepoints, with time relative to first dose. Keep dots small or remove to reduce clutter. See Figure 4.6 from mid207187 Include LOQ line in plot.	SAC [1]

Pharmacokinetic: Figures					
No.	Population	GSK Standard / Example Shell	Title	Programming Notes	Deliverable [Priority]
4.19.	PK	PK17	Mean VH3739937 Plasma Concentration-Time Plots (Linear and Semi-log) – Weekly Dosing Cohort 6	Include all timepoints, with time relative to first dose. Use nominal times in X axis.	SAC [1]
4.20.	PK	PK17	Median VH3739937 Plasma Concentration-Time Plots (Linear and Semi-log) – Weekly Dosing Cohort 6	Include all timepoints, with time relative to first dose. Use nominal times in X axis.	SAC [1]

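### The SAP 8.2 concentration-QTcF model has no treatment, day/time or participant term, so in the once-daily cohorts part of any non-drug drift between Day 1 and Day 14 goes into the concentration slope

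*SAP*

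**What the plan says.** SAP 8.2 specifies "Linear regression models using exposure as the independent variable and change from baseline in QTcF as the outcome variable". The displayed equation has two parameters, an intercept and a coefficient for concentration. The models "will be run separately for Part 1 and 2", and both estimates are reported with 95% confidence intervals. Figures 4.16 and 4.17 (SAP 13.10.7) show the same relation, each titled "Scatter Plot of Individual QTcF Change from Baseline vs Time Matched VH3739937 PK Concentration". They use the PK population, defined in SAP section 4: "The PK Population will include all participants who undergo plasma or urine PK sampling and have evaluable PK assay results". Neither document says whether placebo samples are assayed or set to zero.

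For Cohorts 3 to 5, Protocol 4.1 schedules Holter recordings "on the day before the first dose (Day -1), Day 1, and Day 14 for extraction of ECGs paired with PK sampling". The Schedule of Activities (Table 3 for Cohorts 3 and 4, Table 4 for Cohort 5) confirms this ("Continuous ECG monitoring from Day -1 to 24 h post dose on Day 1 and 14") and calls Day -1 a full time-matched baseline. Each cohort randomizes 7 participants to active drug and 3 to placebo. SAP 5.2 sets the ECG baseline at Day 1 pre-dose.

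On exposure, Protocol 4.1 states: "Due to the observed half-life of ~90 h, the anticipated accumulation ratio following repeated daily and weekly doses is ~6-fold and 1.3-fold, respectively".

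**The concern.** In the once-daily cohorts, day and concentration rise together. Day 1 supplies the low concentrations and Day 14 the high ones. With a Day 1 pre-dose baseline, a Day 14 change contains any shift in QTcF that two weeks of confinement, diet or posture may produce. A model with concentration as its only predictor cannot separate such a shift from a drug effect. An upward drift looks like prolongation, and a downward drift can hide it.

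The design already holds the means of separation: nine placebo participants across Cohorts 3 to 5 on the same recording schedule, and placebo periods within participants in Part 1. The model gives them no role. It also has no participant term, although each Part 2 participant contributes up to 28 post-baseline-definition records (14 time points on two days).

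The use of the data raises the stakes. Protocol 7.1.4 explains its choice of the higher of two animal exposure limits (96.2 rather than 51.9 µg*h/mL) by the need for exposures high enough for cardiodynamic assessment, so as to "mitigate the need for a TQT study". Protocol 8.1.4.1 repeats that aim.

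**Working it through.** **1. The protocol's accumulation figure.** With a half-life of 90 h, k = ln 2 / 90 = 0.00770 per h.

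- Daily dosing, steady state: 1 / (1 − exp(−24k)) = 5.93, which reproduces the stated 6-fold.
- After 14 daily doses: 5.93 × (1 − exp(−14 × 24k)) = 5.48. The simulated Day 14 to Day 1 Cmax ratio is 5.6 to 5.9.
- Weekly dosing, steady state: 1 / (1 − exp(−168k)) = 1.38, against a stated 1.3.

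Cohort 6 has no continuous ECG in its schedule, so the drift question concerns Cohorts 3 to 5.

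**2. Set-up for the slope.**

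- From the protocol: a one-compartment model with first-order absorption (2.2.1); 14 sampling times on Days 1 and 14; 7 active and 3 placebo participants per cohort; median daily AUC of 22.7 and 39.8 µg*h/mL and a 100 mg median Cmax of 1.72 µg/mL (Table 11); between-participant CV of 25 to 50% (Table 8).
- Assumed, because the documents do not give them: absorption rate 0.2 to 1.0 per h; a 25 mg AUC of 11.9 µg*h/mL.
- Imposed: zero drug effect, and 1 ms added to every Day 14 record in both arms.

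The SAP model, change = b0 + b1 × concentration, is fitted by least squares. The fitted change at the 100 mg Cmax is b0 + 1.72 × b1.

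**3. Results per 1 ms of drift.**

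| Model | Slope b1 (ms per µg/mL) | Fitted change at 1.72 µg/mL (ms) |
|---|---|---|
| SAP model, active only, CV 25-50% | 0.49 to 0.66 | 1.05 to 1.27 |
| SAP model, active only, CV 0% | 0.75 to 0.76 | 1.36 to 1.40 |
| SAP model, placebo added at 0, CV 0-50% | positive | 1.01 to 1.28 |
| Treatment and day-by-time terms added, placebo at 0 | 0.00 | 0.00 due to concentration |

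The figures at non-zero CV are averages over simulated trials. The ends of the ranges move by up to 0.04 with the random seed.

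**4. Sensitivity to scaling.** Scaling the profiles to Cmax (0.968 and 1.72 µg/mL from Table 11, 0.53 assumed for 25 mg) gives these results:

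- Active only, CV 0%: slope 0.70 to 0.72, fitted change from 0.092 + 1.201 = 1.29 to 0.074 + 1.231 = 1.31 ms.
- Active only, CV 35%: slope 0.55 to 0.57, fitted change from 0.164 + 0.943 = 1.11 to 0.147 + 0.980 = 1.13 ms.
- Placebo added at 0, CV 35%: fitted change from 0.312 + 0.740 = 1.05 to 0.310 + 0.753 = 1.06 ms.

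The conclusion does not depend on the choice.

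**5. How much of the drift the slope takes.** Multiply the slope by the Day 1 to Day 14 rise in mean concentration (Cmax scaling, CV 0 or 35%). Within one cohort the slope takes about 99% of the drift. With the three cohorts pooled it takes 51 to 64% (active only) or 39 to 49% (placebo at 0), because the spread between doses and the intercept absorb the rest. The fitted change at the top-dose Cmax can still reach or exceed the full drift, since it includes the intercept and lies at the high end of the line.

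**6. Illustration.** For an assumed drift of 2 to 5 ms at CV 25-50%, the false slope runs from 2 × 0.49 = 1.0 to 5 × 0.66 = 3.3 ms per µg/mL. The fitted change at 1.72 µg/mL runs from 2 × 1.05 = 2.1 to 5 × 1.27 = 6.4 ms, with the sign of the drift.

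**The case against.** The strongest reply is that the analysis is exploratory and may not be the one that counts. The endpoint is to be analysed only if development continues. Protocol 9.4.5 allows the PK/PD details to sit in a separate plan, and SAP sections 9 and 10 send pharmacodynamic and PK/PD work elsewhere. This lowers the severity. It does not remove the point: SAP 8.2 writes out this regression and its intervals, and lists Figures 4.16 and 4.17 as deliverables. A reader might infer that this regression is itself the planned substitute for a TQT study. The documents do not support that, because Protocol 7.1.4 ties exposure and cardiodynamic assessment in general to that aim, and the governing model may be in another plan.

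A reader might also infer that placebo participants are left out. The SAP does not say so. Its PK population neither names nor excludes them, and the blinded schedules draw PK samples without an active/placebo split. Inclusion alone would not help, as the third row of the table shows. The cause is the missing terms.

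A third stronger reading, that all drift is taken as drug effect, also fails. Pooled over doses, the slope takes roughly half to two thirds of it with active records only.

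Other displays offer some protection. Tables 3.32 to 3.34 summarize ECG data in the Safety population, where placebo is a display group, so a placebo drift might be noticed. They do not correct the slope. Finally, the zero in the last row follows by construction, because the same drift was imposed on both arms. It shows that the terms remove a shared drift, not one that differs by arm.

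**Conclusion.** The point holds as a defect of model specification. As written, SAP 8.2 cannot separate a shared Day 1 to Day 14 drift from a concentration effect in Cohorts 3 to 5. Each 1 ms of drift produces a false slope of about 0.5 to 0.66 ms per µg/mL and a false fitted change of about 1.05 to 1.27 ms at the 100 mg median Cmax, at the protocol's own range of between-participant variability. With no such variability the figures are about 0.75 and 1.4. The direction follows the drift.

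These sizes rest on the assumed absorption rate, the assumed 25 mg exposure and a drift common to both arms. Nothing in the documents shows that drift exists or how large it would be. In Part 1 the same terms are missing, but no size is claimed there. The change should be made, with a severity that reflects the exploratory status.

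**What to change.** In SAP 8.2, before database freeze:

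- Include all Part 1 and Part 2 (Cohorts 3 to 5) participants with paired Holter ECGs, with placebo records at concentration 0.
- Fit a linear mixed model with concentration, treatment (active or placebo), nominal day-by-time as categories (period-by-time in Part 1) and a participant random effect.
- Report the placebo-corrected predicted change at the observed Cmax, with its interval.
- State which baseline applies. SAP 5.2 uses Day 1 pre-dose, while a time-matched Day -1 recording is also collected. A Day -1 baseline would address time of day but not drift to Day 14.
- Change the population for Figures 4.16 and 4.17 to match.
- State whether SAP 8.2 or the separate PK/PD plan allowed by Protocol 9.4.5 and SAP section 10 governs.

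The ECGs are already scheduled, and placebo concentrations can be set to zero without assay. The cost is SAP wording and a few more terms in an exploratory model. Those terms take up some of the information on concentration, so the slope may be less precise.

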Psychiatric AEs were reported in 2 of 16 participants from Part 1 and in 6 of 56 participants from Part 2 of the study. All these events were mild (except 1 event of depression in Part 1 that was moderate in intensity in a participant with history of family stressors prior to study entry) and none were considered related to the study treatment.

Neurologic AE of headache was reported in 6 participants from Part 1 and in 15 participants from Part 2. There were no major GSK3640254 related neuro/psychiatric events observed. None of these events (except 1 in Part 2) were considered related to the study treatment.

Skin tissue disorders AEs, contact dermatitis due to ECG leads were reported in 5 out of 16 participants in Part 1. In Part 2, 14 out of 56 participants reported skin related AEs, contact dermatitis due to ECG leads n=8, dry skin, eczema nummular, miliaria, pruritus rash and rash maculo-papular. All events were mild in intensity and none was considered related to study treatment. One event lead to study discontinuation (rash maculo-papular).

Though there were a number of participants with ECG abnormalities in both parts of the study, none of these findings were considered clinically significant. There were no

clinically significant arrhythmias reported in either Part 1 or Part 2 of the study. No participants had a QT interval corrected for heart rate according to Fridericia's formula (QTcF) value of >500 msec or an increase from baseline >60 msec. A cardiodynamic evaluation of the multiple ascending dose portion of Study 207187 was undertaken based upon concentration vs change from pre-dose QT interval corrected (QTc) using 12-lead Holter ECGs an analysis by iCardiac/eRT. This indicated a weak relationship between QT prolongation and GSK3640254 plasma concentrations and indicated that an effect on QTcF can be excluded up to GSK3640254 plasma concentration of ~2000 ng/mL [GlaxoSmithKline Document Number [2018N392814_01](#)].

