8.1.4.1. Cardiodynamic assessment (ECGs extracted from Holter recordings)

The frequency of ECG data in the SAD and MAD arises from emerging literature suggesting frequent QT evaluation early in development may mitigate the need for a formal TQT study [Darlo, 2014]. ECGs will be extracted as shown in the [SoA](#) from the SAD and the MAD component of the study. Should clinical development of VH3739937 continue, an exploratory objective of this study is to assess the exposure-response relationship between VH3739937 and QTcF following single and repeat dose administration.

The 12-lead Holter and ECG equipment will be used and may be supplied and supported by eREsearchTechnology, Inc. (ERT) or the contract research organization (CRO). All ECG data will be collected using a Global Instrumentation (Manlius, NY, USA) M12R ECG continuous 12 lead digital recorder. The continuous 12-lead digital ECG data will be stored onto SD memory cards. ECGs to be used in the analyses will be selected by pre-determined time points as defined in the [SoA](#), and will be read centrally by ERT, Inc.

The following principals will be followed in ERT's core laboratory:

- ECG analysts are blinded to the subject, visit and treatment allocation
- Baseline and on-treatment ECGs for a particular subject will be over-read on the same lead and will be analyzed by the same reader.
- The primary analysis lead is lead II. If lead II is not analyzable, then primary lead of analysis will be changed to another lead for the entire subject data set.

The following is a brief description of ECG analysis methods utilized by ERT's core laboratory.

TQT Plus ECG Extraction Technique

Ten 14-second digital 12-lead ECG tracings will be extracted from the continuous Holter recordings using the 'TQT Plus method', a computer-assisted and statistical process utilized by ERT, Inc. The method enables extraction of ECGs with the lowest heart rate (HR) variability and noise within the protocol-specified extraction time window (e.g., the HR and QT changes from beat-to-beat in the range of <10%). At each protocol-specified timepoint, 10 ECG replicates will be extracted from a 5-minute "ECG window" (typically, the last 5 minutes of the 15-minute period when the subject is maintained in a supine or semi-recumbent quiet position).

High-Precision QT Analysis

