4.11.	PK	PK24	Plasma VH3739937 Trough Concentration-Time Plots (Linear and Semi-Log) by Cohort by Day - Part 2	
All Subjects Overlay - Days 1 Through 14 for Cohort (3 and 4) Days 1-18 for Cohort 5. All points for Cohort 6
 
Trough Concentrations Only
 
Add footnote: For Cohort 3 and 4 Pre-dose (trough) concentrations shown for days 1-14. Last dose taken on Day 14. Days 15-19 are follow-up visits.
 
For Cohort 5: Pre-dose (trough) concentrations shown for days 1-18. Last dose taken on Day 18. Days 19-23 are follow-up visits.
 
See fig 4.62 from mid207187
	

Pharmacokinetic: Figures					
No.	Population	GSK Standard / Example Shell	Title	Programming Notes	Deliverable [Priority]
Relative Bioavailability/Food Effect					
4.12.	PK	PK28	Geometric Mean Treatment Ratio and 90% Confidence Interval of VH3739937 PK Parameters for Relative Bioavailability	Stats output: use mean from Table 4.12 See Reference Figure 4.4 from mid208131 PK Parameters: $AUC_{(0-24)}$, $AUC_{(0-\infty)}$, and C_{max} Ratio: Test/Reference (Tablet/PiB)	SAC [1]
4.13.	PK	PK28	Geometric Mean Treatment Ratio and 90% Confidence Interval of VH3739937 PK Parameters for Food Effect	Stats output: use mean from Table 4.13 See Reference Figure 4.4 from mid208131 PK Parameters: $AUC_{(0-24)}$, $AUC_{(0-\infty)}$, and C_{max} Ratio: Test/Reference (Tablet Fed/Tablet Fasted)	SAC [1]
4.14.	PK	PK25	Comparative Plot of Individual Plasma VH3739937 PK Parameters for Relative Bioavailability by Treatment (Linear and Semi-log)	PK Parameters: $AUC_{(0-24)}$, $AUC_{(0-\infty)}$, and C_{max} Treatments and positioning: PiB Fed on left, Tablet Fed on right.	SAC [1]

Pharmacokinetic: Figures					
No.	Population	GSK Standard / Example Shell	Title	Programming Notes	Deliverable [Priority]
4.15.	PK	PK25	Comparative Plot of Individual Plasma VH3739937 PK Parameters for Food Effect by Treatment (Linear and Semi-log)	PK Parameters: AUC ₍₀₋₂₄₎ , AUC _(0-inf) , and C _{max} Treatments and positioning: Tablet Fasted on left, Tablet Fed on Right side	SAC [1]
4.16.	PK	PK_F1	Scatter Plot of Individual QTcF Change from Baseline vs Time Matched VH3739937 PK Concentration – Part 1	Stats Output (for regression) Non-Standard Figure See shell at end of RAP, Reference study mid207187 Figure 5.1, Overlay regression line and 95% CI, print Beta regression line on plot.	SAC [1]

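### SAP 8.2 plans no predicted QTcF change at Cmax with a confidence bound and names no effect size to exclude, although the protocol wants the QT data to help mitigate the need for a TQT study

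*SAP*

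**What the plan says.** **Purpose.** Protocol 7.1.4 gives the LOAEL AUC as 96.2 µg*h/mL in rats and 51.9 in dogs, and states: "The LOAEL in rats was chosen as the PK stopping criteria". Its reason for taking the higher value is the "need to achieve sufficiently high exposures for cardiodynamic assessment of the TQT prolongation risk and mitigate the need for a TQT study". Section 8.1.4.1 supports the ECG schedule with literature suggesting that "frequent QT evaluation early in development may mitigate the need for a formal TQT study". For the related compound GSK3640254, Protocol 2.2.1 reports a cardiodynamic analysis that "indicated that an effect on QTcF can be excluded up to GSK3640254 plasma concentration of ~2000 ng/mL".

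**Status.** The QT objective is exploratory and conditional: "Should clinical development of VH3739937 continue, an exploratory objective of this study is to assess the exposure-response relationship".

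**Analysis.** SAP 8.2 fits a straight line of change in QTcF on concentration, separately for Parts 1 and 2. Its equation contains an intercept and a slope and nothing else. For these two estimates it says: "and their 95% confidence intervals will be reported, and the regression line will be overlayed on the plot".

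**Displays.** SAP 13.10.7 asks for this in Figure 4.16 (Part 1): "Overlay regression line and 95% CI, print Beta regression line on plot". The note for Figure 4.17 (Part 2) reads only: "Non-Standard Figure see shell at end of RAP, Reference study mid207187 Figure 5.2". Both figures use shell PK_F1, which is not reproduced in the SAP. Tables 3.32 to 3.34 summarise ECG and QTc values by category and by visit.

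**Separate plan.** Protocol 9.4.5 leaves PK/PD details to the RAP or to a separate plan. SAP sections 9 and 10 say that pharmacodynamic and PK/PD analyses are reported separately.

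**The concern.** The protocol's purpose implies a question about exclusion: up to what concentration can a QTcF effect of a given size be ruled out? The related compound's result is worded in exactly that form. Intercept and slope CIs do not state an answer. A slope CI that covers zero does not rule out an important effect, and one that misses zero does not establish an important effect. To make an exclusion statement someone must choose a concentration, a confidence bound and a limit, and none of the three is written down. If they are chosen after the line has been seen, the statement loses much of its value. That matters because the same assessment is cited to justify an exposure limit in healthy participants.

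**Working it through.** The documents give no sample size, power, margin or QTcF SD for this analysis, so there is no planned figure to reproduce.

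**1. The exposure premise.** 96.2 / 51.9 = 1.85, so the chosen AUC limit is 1.85 times the alternative LOAEL. The projected median Cmax is 1.72 µg/mL at 100 mg QD (Protocol Table 11) and 1.60 µg/mL at 800 mg single dose (Protocol 4.3.3). Their ratio is 1.72 / 1.60 = 1.075, so Part 2 has the higher projected Cmax, by about 7%.

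**2. Planned output against the question.**

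| Needed for an exclusion statement | Written in the documents |
|---|---|
| Predicted QTcF change at a named concentration | No |
| Confidence bound for it | Partly: 95% CI overlay on Figure 4.16; not repeated in the Figure 4.17 note |
| Effect size to exclude | No |
| Rule for concluding exclusion | No |

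**3. What would answer it.** With intercept b0 and slope b1, the upper bound at concentration C is U(C) = b0 + b1·C + t × SE(b0 + b1·C). If the change is taken relative to zero concentration, it is U(C) = C × [b1 + t × SE(b1)]. An effect of size L is excluded up to the highest observed C at which U(C) < L. Either version comes from the fit already planned.

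**4. Illustration only.** This shows that slope significance and exclusion are different conclusions. It does not predict this trial.

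- From the documents: 7 active participants at each of 25, 50 and 100 mg QD, 9 placebo, Days 1 and 14, 13 post-dose times, half-life 90 h, and Cmax ratio 0.968 / 1.72 = 0.56 for 50 against 100 mg.
- Assumed: limit 10 ms at 1.72 µg/mL, absorption rate 0.5/h, 25 mg at 0.30 of the 100 mg exposure, exposure log-SD 0.27, and the SDs in the table.
- Method: 1,000 trials per cell, cluster-robust errors (29 df), slope 95% CI, and the upper limit of the two-sided 90% CI of b0 + b1 × 1.72.

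| SD participant / day / residual (ms) | True 10 ms: slope CI covers zero | True 10 ms: bound below 10 ms | True 5 ms: slope significant, 10 ms excluded | True 5 ms: slope not significant, 10 ms not excluded |
|---|---|---|---|---|
| 4 / 3 / 5 | 0.3% | 6% | 64% | 0.2% |
| 6 / 5 / 8 | 9% | 6% | 19% | 11% |
| 8 / 7 / 10 | 29% | 6% | 3% | 32% |

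Repeat runs moved entries by up to about 4 percentage points. The 6% is close to the nominal 5% of the one-sided bound. Table 11's 1.72 applies after the last dose (Day 18), while the last Holter is on Day 14. At a 90 h half-life the fraction of steady state is 0.925 on Day 14 and 0.964 on Day 18, a ratio of 0.96, which is immaterial here.

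**5. Standard errors.** SAP 8.2's equation has no participant term. A second illustration used a true effect of zero, 14 time points on two days (21 × 28 = 588 pairs without placebo, 30 × 28 = 840 with), a 25 mg Cmax of 0.52 µg/mL, Cmax CV 35%, and SDs from 3/2/4 to 7/5/8 ms. Ordinary least squares gave a 95% half-width at 1.72 µg/mL of about 0.8 to 1.9 ms. The actual sampling half-width was about 2.4 to 5.7 ms, and the nominal 95% interval missed the truth in about 45% to 53% of trials. A bound taken from the model as written would be too narrow under these assumptions.

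**The case against.** The other side has real substance.

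- **A separate plan may hold the rule.** Protocol 9.4.5 and SAP sections 9 and 10 point to one. It was not supplied, so absence from SAP 8.2 is not absence from the programme. This stands, and it limits the point to what is written here. SAP 8.2 does not cite a plan containing a bound or a limit.
- **Figure 4.16 has a band.** If it is the usual pointwise band, a Part 1 bound can be read at any observed concentration. Figure 4.17 shares shell PK_F1, so a reader might infer that Part 2 has no band, but the unseen shell prevents that conclusion. What stands is that the instruction is not repeated.
- **The SAP never says that a slope CI covering zero excludes an effect.** Correct. The simulation contrasts two ways of reading the output and does not test a planned rule.
- **The bound can be derived later without new data.** True of the bound, but not of a limit fixed in advance.
- **Status.** The objective is exploratory and conditional, Protocol 9.1 tests no formal hypotheses, and participant safety rests on the QTc stopping criteria, not on this regression. This lowers the priority.

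A reader might also infer that the two reported CIs can never be turned into a bound. The documents do not support that: the change relative to zero concentration is slope × Cmax, so its bound follows directly from the slope CI.

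**Conclusion.** The point holds in limited form. The protocol gives mitigation of a TQT study as part of the reason for its MAD exposure limit and ECG sampling. The written concentration-QTc analysis plans no predicted change at Cmax with a bound and names no effect size to exclude. It should be treated as a cheap improvement.

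Three stronger readings are not supported. The plan is not shown to be unable to exclude a QT effect, because the fitted model can yield the bound. SAP 8.2 is not the only QT analysis, because Tables 3.32 to 3.34 also summarise QTc. The protocol does not raise a dose for this purpose: it sets a higher stopping limit, and the projected median AUC at 100 mg QD (39.8 µg*h/mL) lies below even the lower LOAEL of 51.9, although its upper bound (62.0) does not.

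No pass or fail result can be calculated. The 0.3% to 29% range depends on the assumed 10 ms limit and assumed SDs.

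**What to change.** In SAP 8.2, or in the separate PK/PD plan with a citation from 8.2:

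1. For Parts 1 and 2 separately, report the model-predicted QTcF change at the geometric mean Cmax of each dose level, with a two-sided 90% CI. In Part 2 use Day 1 and Day 14, the Holter days of Cohorts 3 to 5. State whether the prediction includes the intercept or is relative to zero concentration.
2. Use standard errors that respect repeated readings per participant.
3. State in advance the effect size that the sponsor wants to exclude. The documents give none, so the choice is the sponsor's.
4. Base any exclusion statement on the upper bound, up to the highest observed concentration at which it stays below the limit, and not on whether the slope CI covers zero.
5. Ask for the confidence band in the notes for both Figures 4.16 and 4.17.

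The cost is a few sentences and one estimate statement per model, with no new data, visits or participants. The downside is that a limit fixed beforehand may leave the result reading as not excluded.
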